11.2.3 Disposition of Study Subjects

Subject disposition will be summarized using counts and percentages. The number and percentage of subjects completed and discontinued along with the specific reasons for discontinuation will be tabulated by randomized treatment group and in total.

11.2.4 Demographic, Baseline, and Clinical Characteristics

Summary statistics will be provided for patient demographics and baseline characteristics by randomized treatment group and in total. These characteristics will be compared between treatment groups using Fisher's Exact test for categorical variables and the two-sample t-test or Wilcoxon Rank Sum test for continuous variables.

11.2.5 Efficacy Analyses

Primary Endpoint

The time to hemostasis will be measured from start of study treatment to the achievement of hemostasis at the target bleeding site (TBS), or to the end of the 10-minute observation period. The time to hemostasis will be considered as censored at the end of the 10-minute observation period. Time to hemostasis will be quantified in minutes according to its nominal time point. When re-bleeding occurs, and the cessation of bleeding is again achieved at a later time point, the effective time to hemostasis will be the latter time point. The time to hemostasis will be the time from start of study treatment to that last effective hemostatic time point.

Secondary Endpoints

- Percentage of subjects achieving hemostasis at the target bleeding site at 2 minutes and at 5 minutes following the start of study treatment;
- Percentage of subjects with intraoperative hemostasis at the target bleeding site;
- Percentage of subjects with intraoperative re-bleeding from the target bleeding site post hemostasis;
- Postoperative re-bleeding from the target bleeding site requiring surgical re-exploration up to 30 days after surgery.

Analysis of the Primary Endpoint

The primary endpoint analyses will be based on ITT population. The primary analysis is the test of non-inferiority of HemoStyp compared with Surgicel. Cox proportional hazards regression or log-rank test will be used for the analysis of non-inferiority.

The null hypothesis for the testing of the primary endpoint is described below:

H0: HemoStyp is inferior or worse than Surgicel by more than 1 minute for median survival (HR<0.8);

H1: HemoStyp is inferior to Surgicel by less than 1 minute for median survival (HemoStyp is not inferior to Surgicel) ($HR > 0.8$);

If the lower bound 95% confidence interval of $HR > 0.8$, we conclude that HemoStyp is not inferior to Surgicel.

The primary endpoint analyses will also be performed on the PP population.

Analyses of Secondary Endpoints

A two-sided z-test with pooled variance will be used to test the difference for each secondary endpoint. The 95% confidence intervals (CIs) for each secondary endpoint in each group (HemoStyp or Surgicel) will be provided.

Secondary endpoints will be assessed at significant level of 0.05 in the order listed below after achievement of a significant result for the primary endpoint:

- 1) Percentage of subjects achieving hemostasis at the target bleeding site at 3 minutes following the start of study treatment
- 2) Percentage of subjects with intraoperative hemostasis at the target bleeding site;
- 3) Percentage of subjects with intraoperative re-bleeding from the target bleeding site post hemostasis;
- 4) Percentage of subjects with postoperative re-bleeding from the target bleeding site requiring surgical re-exploration up to 30 days after surgery
- 5) Percentage of subjects achieving hemostasis at the target bleeding site at 5 minutes following the start of study treatment
- 6) Percentage of subjects achieving hemostasis at the target bleeding site at 10 minutes following the start of study treatment

The null hypothesis for the testing of the secondary endpoints is described below:

$H_0: \mu_0 = \mu_1$

$H_1: \mu_0 \neq \mu_1$,

μ_0 and μ_1 are the percentages for each of the secondary endpoints in HemoStyp group and Surgicel group, respectively.

Analyses of Subgroups

To assess homogeneity of treatment effectiveness, subgroup analyses will be assessed for the following subgroups with a significance level of 15%:

-

- Male vs. Female
- Groups based on target bleeding sites
- Groups based on types of surgery
- Groups based on Lewis bleeding scale

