A two-sided z-test with pooled variance will be used to test the difference for each secondary endpoint. The 95% confidence intervals (CIs) for each secondary endpoint in each group (HemoStyp or Surgical) will be provided. The secondary endpoints will be assessed at the significant level of 0.05 in a defined order after achievement of a significant result for the primary endpoint .

To assess homogeneity of treatment effectiveness, subgroup analyses will be performed.

Interim Analysis

After 118 randomized subjects have been seen at 30 day visit.

Safety Analyses

Safety analysis will be performed on the safety population using descriptive statistics without inferential tests for significance. Safety evaluation will include monitoring of adverse events (adverse events/serious adverse events [SAEs]) and adverse device effects (ADEs). Adverse events will be coded using the current version of the Medical Dictionary for Regulatory Activities (MedDRA). Treatment-emergent adverse events will be presented in summary tables by system organ class (SOC), preferred term and by treatment group. The number and percentage of subjects within each SOC and preferred term and the number of adverse events within each SOC and preferred term will be presented. The summary of adverse events by severity will be tabulated. The summary of adverse events by causality will also be provided. For each patient and each adverse event, the worst severity and causality recorded will be used in the by-intensity and by-relationship summaries.

Table 1.1 Schedule of Evaluations

	Screening	Surgery	Post-surgical Follow Up
Visit	V1	(Randomization) V2	V3
Trial Day	Day -10 to 0	Day 0	Day 30 ± 7
Informed consent	X		
Inclusion / Exclusion criteria	X	X	
Demographics	X		
Medical history	X		
Concomitant medication review	X	X	X
Vital signs	X		
Height and Weight	X		
Laboratory Measures ¹	X		
Urine pregnancy test ²	X		
Surgery performed		X	
Appropriate target bleeding sites identified ³		X	
Randomization		X	
Treatment applied to target bleeding sites		X	
Time to hemostasis of target bleeding sites		X	
Assess for re-bleeding or post-surgical re-bleeding		X-----X	X
Adverse events review		X	X

1. Laboratory parameters obtained for subjects as pre-operation standard of care that include a complete blood count (CBC) and may include prothrombin time (PT) and partial thromboplastin time (PTT) reflecting patients medical and medication history.

2. Obtained for women of child-bearing potential.

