11 STATISTICAL AND ANALYTICAL PLANS

A detailed Statistical Analysis Plan (SAP) will be written and approved prior to database lock. The SAP will describe all planned analyses based on the statistical design of this study and the subsequent data collected. A brief overview of key statistical analyses is provided below.

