11.1 Determination of Sample Size

A non-inferiority comparison will be performed to determine if the hazard ratio with an overall sample size of 212 subjects (106 HemoStyp group and 106 Surgicel group) achieves 80% power at a 0.05 significance level when the hazard ratio is actually 1.33 (median survival is 3.0 minutes for HemoStyp and 4.0 minutes for Surgicel). The non-inferiority ratio is 0.75 (corresponding to margin of 1 minute). It is anticipated that the proportion of subjects observed with the event during the study is 0.90 for the HemoStyp group and 0.92 for the Surgicel group. These results assume that the hazard ratio is constant throughout the study and that Cox proportional hazards regression or the non-inferiority log-rank test is used to analyze the data.

It is anticipated that approximately 710 subjects will be screened to randomize approximately 236 subjects with an anticipated drop-out rate of approximately 10%.

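### The trial is sized on a non-inferiority hazard ratio of 0.75 but judged against 0.80, and both are called 1 minute

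*Combined protocol and SAP*

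**What the plan says.** Section 11.2.5, under the analysis of the primary endpoint, gives the null hypothesis as "H0: HemoStyp is inferior or worse than Surgicel by more than 1 minute for median survival (HR<0.8"). The alternative uses the same 0.8 and the same 1-minute description. The success rule is "If the lower bound 95% confidence interval of $HR > 0.8$, we conclude that HemoStyp is not inferior to Surgicel".

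Section 11.1, repeated in the synopsis, gives a different threshold: "The non-inferiority ratio is 0.75 (corresponding to margin of 1 minute"). The planned effect there is that "the hazard ratio is actually 1.33 (median survival is 3.0 minutes for HemoStyp and 4.0 minutes for Surgicel"). The claim for 106 subjects per arm is that the design "achieves 80% power at a 0.05 significance level", with expected event proportions of "0.90 for the HemoStyp group and 0.92 for the Surgicel group".

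Two other statements bear on the rule. The synopsis gives the timing of an interim analysis, "After 118 randomized subjects have been seen at 30 day visit", and nothing else about it. Section 11 says that "A detailed Statistical Analysis Plan (SAP) will be written and approved prior to database lock". The summary of changes in section 14.15 does not mention the margin, so the conflict lies within current text.

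**The concern.** One primary test has two thresholds with the same clinical label. A result between them would succeed on the margin used for sizing and fail on the margin in the decision rule. This is an open-label pivotal trial meant to support a marketing application, with an interim look planned and a detailed SAP that need only be approved before database lock. If the margin is settled late, the choice could be made, or appear to have been made, with results in view.

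The decision rule has two further gaps. It does not say whether the 95% bound is one- or two-sided, and section 11.1 gives only a 0.05 level. The plan also does not say whether non-inferiority may be claimed at the interim look.

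**Working it through.** **Inputs (section 11.1 unless noted).** Medians 3.0 minutes (HemoStyp) and 4.0 minutes (Surgicel); hazard ratio (HR) 1.33, above 1 favouring HemoStyp; 106 per arm; event proportions 0.90 and 0.92; margin 0.75 (11.1) or 0.80 (11.2.5); censoring at 10 minutes (11.2.5). The sidedness of the bound is not given, so both readings are shown: z = 1.960 (two-sided 95%) and z = 1.645 (one-sided 95%).

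**1. The plan's power figure.** Expected events d = 106 × 0.90 + 106 × 0.92 = 192.9. Chance of claiming non-inferiority = Φ(½√d × ln(HR/margin) − z). At HR 1.33:

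| Margin | Two-sided 95% | One-sided 95% |
|---|---|---|
| 0.75 | 97.8% | 99.0% |
| 0.80 | 94.2% | 97.0% |

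Neither row gives 80%. Total N for 80% power = 4(z + 0.842)² / ln(1.33/margin)² / 0.91:

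| Margin | Two-sided 95% | One-sided 95% |
|---|---|---|
| 0.75 | 105.1 | 82.8 |
| 0.80 | 133.5 | 105.2 |

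A total of about 106 fits 0.75 two-sided and 0.80 one-sided equally well, so the stated sample size does not show which margin was used.

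**2. What 1 minute means.** The plan takes HR = Surgicel median / HemoStyp median (4.0/3.0 = 1.33), as for exponential times. With Surgicel at 4.0 minutes:
- HR 0.80: HemoStyp median 4.0/0.80 = 5.00, which is 1.00 minute worse.
- HR 0.75: 4.0/0.75 = 5.33, which is 1.33 minutes worse.

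A ratio of 0.75 equals 1 minute only if the Surgicel median is 3.0 (3.0/0.75 = 4.0), but the plan gives 3.0 to HemoStyp.

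**3. Event proportions.** Under exponential times the proportion with hemostasis by 10 minutes is 1 − 2^(−10/median): 0.901 for a 3.0-minute median, 0.823 for 4.0 and 0.750 for 5.0. The stated 0.90 for HemoStyp fits; the stated 0.92 for Surgicel does not. On exponential proportions, 212 subjects give about 183 events at HR 1.33, 175 at HR 1.0 and 167 at HR 0.80. Ranges below run between these counts and 193.

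**4. Results in dispute.** Observed HR needed = margin × exp(2z/√d):

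| Events | Two-sided: 0.75 / 0.80 | One-sided: 0.75 / 0.80 |
|---|---|---|
| 193 | 0.995 / 1.061 | 0.950 / 1.014 |
| 175 | 1.009 / 1.076 | 0.962 / 1.026 |

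**5. Chance of claiming non-inferiority under each margin.**

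| True HR | Bound | At 0.75 | At 0.80 | Between the margins |
|---|---|---|---|---|
| 0.80 | two-sided | 6.1-6.5% | 2.5% | 3.6-4.0% |
| 0.80 | one-sided | 11.0-11.6% | 5.0% | 6.0-6.6% |
| 1.00 | two-sided | 48-52% | 31-34% | 16-17% |
| 1.00 | one-sided | 60-64% | 43-46% | 17-18% |
| 1.33 | two-sided | 97-98% | 93-94% | about 4% |
| 1.33 | one-sided | 99% | 96-97% | about 2% |

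A simulation agrees (10,000 trials, exponential times read on the 30-second grid, censored at 10 minutes, Cox model with Efron ties, 106 per arm). With a two-sided bound, the chances at 0.75 and 0.80 were 6.2% and 2.7% at HR 0.80, 47.7% and 31.3% at HR 1.0, and 97.2% and 93.0% at HR 1.33.

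**6. If a claim were allowed at either look without adjustment.** This is an assumption; the plan does not say so. With an information fraction of 118/236 = 0.50 to 118/212 = 0.557 and a bivariate normal calculation, the error rate at HR 0.80 against the 0.80 margin rises from 2.5% to 4.1-4.2%, or from 5% to 7.8-8.0%.

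**The case against.** The strongest reply is that section 11.2.5 is the operative text and agrees with itself. Its hypotheses and decision rule all use 0.8, which is the stricter value and the one that matches 1 minute. An analyst following it would apply 0.8, and on the planned HR of 1.33 the trial stays well powered, with only a 2-4% chance of a disputed result. The 16-18% figure needs equal products, which the plan does not assume. All of this stands, and it limits the harm to an ambiguous success criterion and a wrong sizing paragraph.

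The failed 80% is also partly a separate defect, since it does not describe the 0.75 test either. That is right: the margin mismatch alone does not explain it.

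The interim figures rest on an assumed rule. The plan gives only the timing, and a 30-day trigger is later than a 10-minute endpoint needs, so the look may not concern efficacy at all. The figures are therefore conditional. Sidedness and interim alpha could be left to the SAP, but the protocol allows that document to be approved after the interim look.

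Finally, if all 236 randomized subjects contribute, events rise to 236 × 0.91 = 215. The disputed range becomes 0.980-1.045 (two-sided) or 0.939-1.001 (one-sided), and power at equality against 0.80 becomes 37% or 50%. The conclusion does not change.

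**Conclusion.** The contradiction is real and must be resolved: 0.75 in the synopsis and section 11.1, 0.80 in section 11.2.5, both labelled 1 minute. On the plan's own conversion only 0.80 earns that label. The conversion assumes proportional, exponential hazards and a 4.0-minute Surgicel median, as the plan's 1.33 does.

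The disputed range of observed hazard ratios lies around 1, where two similar products could fall. If HemoStyp is truly 1 minute worse, using 0.75 instead of 0.80 raises the chance of a non-inferiority claim by a factor of about 2.2 to 2.6. The trial is not underpowered at the planned effect under either margin, and the written rule is not lenient. The stated 80% power for 212 subjects is wrong for both margins.

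**What to change.** Before any outcome data are seen, including those for the interim look at 118 subjects:

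- **One margin.** In the synopsis and section 11.1, replace 0.75 with 0.80. Suggested wording: *The non-inferiority margin is a hazard ratio (HemoStyp versus Surgicel) of 0.80, which is 1 minute if the Surgicel median is 4.0 minutes and times are exponential.* If the sponsor meant 0.75, it should instead change section 11.2.5, drop the 1-minute label and justify the looser margin. Either choice needs a justification, because the documents give none.
- **Sidedness.** In section 11.2.5, state whether the 95% bound is one- or two-sided. Two-sided (one-sided alpha 0.025) is the stricter reading.
- **Interim.** State that the interim analysis cannot support an efficacy claim, or adjust alpha for it.
- **Power.** Restate power and sample size for the chosen margin and sidedness from one consistent set of medians, hazard ratio and event proportions. Resolve the 0.92 for Surgicel, and check whether a total of 106 was entered as a per-arm figure.

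The cost is wording in three places, carried into the SAP. On the plan's assumptions no patients are added. The price of 0.80 is less room if HemoStyp's advantage is smaller than planned. With 212 subjects, 80% power holds down to a true HR of 0.80 × exp(2(z + 0.842)/√d), which is about 1.20-1.22 (two-sided) or 1.14-1.17 (one-sided). If the products are only equal, power is the 31-34% or 43-46% shown above.

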4.1.2 Scientific Rationale for Study Design

This is a multi-center, open-blind study assigned randomly to 2 treatments (HemoStyp or Surgicel) in a 1:1 ratio. This study is designed to compare HemoStyp with Surgicel, which represents the current standard of care for control of mild to moderate bleeding in an intra-operative setting.

The primary outcome measure for this study is the median time to achieve hemostasis. This is a clinically appropriate outcome measurement in a surgical setting and will assess the whether HemoStyp is non-inferior to Surgicel in terms of the key parameter of median time to achieve hemostasis at target bleeding sites. This study will also evaluate the categorical parameters, namely the percentage of subjects achieving hemostasis at pre-specified time intervals (30 second intervals from application through 10 minutes). In addition, this study appropriately evaluates the percentage of subjects with re-bleeding events during surgery and any post-surgical events requiring additional surgery during a 30-day follow-up period.

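### The hypotheses are written as a 1-minute difference in medians but decided on a hazard ratio of 0.8; the two agree only for constant hazards and a Surgicel median of 4.0 minutes, which the plan's own figures do not fit

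*Combined protocol and SAP*

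**What the plan says.** Section 4.1.2 fixes the quantity of interest: "The primary outcome measure for this study is the median time to achieve hemostasis". Section 11.2.5 writes both hypotheses in minutes of median, each with an HR in brackets. The null is "HemoStyp is inferior or worse than Surgicel by more than 1 minute for median survival (HR<0.8"; the alternative is "HemoStyp is inferior to Surgicel by less than 1 minute for median survival (HemoStyp is not inferior to Surgicel", paired with an HR above 0.8.

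The test is on another scale. Section 11.2.5 says "Cox proportional hazards regression or log-rank test will be used for the analysis of non-inferiority", and the rule is that if the lower 95% confidence bound of the HR is above 0.8, "we conclude that HemoStyp is not inferior to Surgicel". No criterion involves the medians.

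Section 11.1 gives the planning values: medians of 3.0 minutes (HemoStyp) and 4.0 minutes (Surgicel), with 90% and 92% of subjects having the event. It adds "These results assume that the hazard ratio is constant throughout the study". The plan contains no check of that assumption, no fallback if it fails, and no confidence interval for the difference in medians.

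**The concern.** An HR and a difference in medians are different quantities. One converts to the other only through the shape and location of the time-to-hemostasis distribution. If the conversion fails, the null hypothesis on paper is not the one tested. A result then cannot be read as being about 1 minute, in either direction: the rule may be laxer or stricter than the stated margin.

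This matters because it is the primary hypothesis of a pivotal trial meant to support a marketing application. If the scale is settled only after the data are seen, the choice between minutes and HR becomes data-driven.

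**Working it through.** **Inputs.** From section 11.1: Surgicel median 4.0, HemoStyp median 3.0, event proportions 0.92 and 0.90, 212 subjects (106 per arm). From section 11.2.5: HR margin 0.8, 95% CI. From sections 7 and 11.2.5: inspection every 30 seconds, censoring at 10 minutes. I read the event proportions as those reached by 10 minutes. Surgicel medians other than 4.0, the Weibull shape and the crossing-hazards shape are assumptions.

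**1. The plan's equivalence.** With constant hazards, HemoStyp median = Surgicel median / HR. At 4.0 minutes, 4.0/0.8 − 4.0 = 1.0 minute. The figure reproduces.

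**2. Other Surgicel medians, still constant hazards.** The difference at HR 0.8 is M/0.8 − M = 0.25M: 0.50 minutes at M = 2, 0.75 at 3, 1.00 at 4, 1.50 at 6.

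**3. Do the plan's Surgicel figures fit constant hazards?** A constant hazard with median 4.0 gives 1 − 2^(−10/4) = 82.3% by 10 minutes, against 92% in the plan. HemoStyp's figures do fit: 1 − 2^(−10/3) = 90.1%, against 90%.

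**4. A Weibull curve through both Surgicel figures.** Shape k = ln[−ln(0.08)/ln 2] / ln(10/4) = 1.41. With hazards still proportional, the HemoStyp median at HR 0.8 is 4.0 × 0.8^(−1/1.41) = 4.69, a difference of about 0.69 minutes. At this shape HR 0.8 equals 1 minute only if Surgicel's median is about 5.84. For comparison, shape 0.7 gives 1.50 minutes and shape 2 gives 0.47. So proportional hazards with a median of 4.0 does not secure the match.

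**5. Chance of declaring non-inferiority when HemoStyp is exactly 1 minute worse.** Events = 212 × 0.91 = 193, so SE of ln HR = 2/√193 = 0.144. The probability is Φ[ln(HR/0.8)/SE − 1.96].

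| Surgicel v HemoStyp median (min) | Shape | True HR | Formula | Simulation, 106 per arm |
|---|---|---|---|---|
| 3 v 4 | constant | 3/4 = 0.750 | 0.8% | 1.1% |
| 4 v 5 | constant | 4/5 = 0.800 | 2.5% | 2.6% |
| 6 v 7 | constant | 6/7 = 0.857 | 6.0–6.9% | 6.3% |
| 4 v 5 | Weibull 1.41 | 0.8^1.41 = 0.730 | 0.5% | 0.7% |

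For 6 v 7, the lower formula value uses the 139 events expected under exponential times and the upper uses 193. The simulations fit a Cox model with Efron ties on the 30-second grid, 3,000 runs per case. Repeats of 6 v 7 at 118 per arm gave 6.0% and 7.0%.

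**6. Crossing hazards (assumed shape).** Surgicel is exponential with median 4.0. HemoStyp's hazard is 0.07/min to 4 minutes, then 0.35/min. Its median is 4 + (0.693 − 0.28)/0.35 = 5.18, which is 1.18 minutes worse and inside the stated null. At 118 per arm, repeated simulations declared non-inferiority in 33–36% of trials.

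**The case against.** - **The conclusion is not in minutes.** The plan concludes only that HemoStyp is not inferior. That is literally so, but the alternative hypothesis defines non-inferiority as less than 1 minute worse, so the minutes come with it.
- **The rule is demanding.** With 193 events, the lower bound clears 0.8 only if the observed HR exceeds 0.8 × exp(1.96 × 0.144) ≈ 1.06, so HemoStyp must look slightly faster. This stands, and it limits the risk under proportional hazards. It does not protect where the HR and the median point in different directions.
- **Crossing hazards are speculative.** The 33–36% case needs a five-fold hazard jump at 4 minutes in one arm only. Both products are described as oxidized regenerated cellulose, and nothing in the documents points to that shape. This stands: the case shows what can happen, not what is likely.
- **The plan is not silent on minutes.** Section 11.2.1 requires medians and quartiles by arm. The secondary endpoints include hemostasis percentages at fixed times, which would reveal early and late divergence. Section 11 calls itself an overview, with a detailed SAP to follow. All true. What is missing is narrower: an interval for the median difference and a proportionality check.

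A reader might also infer that crossing hazards make a false claim almost certain. A HemoStyp hazard of 0.10/min to 4.5 minutes, then 0.50/min, is declared non-inferior in about 86% of trials. But its median is 4.5 + (0.693 − 0.45)/0.50 = 4.986, only 0.986 minutes worse than 4.0. That lies inside the stated alternative, so the declaration is correct under the plan's own hypotheses.

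**Conclusion.** The stated null hypothesis is not the one tested, and the equivalence offered between the two fails on the plan's own Surgicel figures.

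It is tempting to infer that the 0.8 rule is generally too lenient. The documents do not support that. With constant hazards the rule is stricter than 1 minute whenever Surgicel's median is below 4.0. Under the shape implied by 4.0 minutes and 92%, it is also stricter at 4.0 itself. It is more lenient if Surgicel is slower than 4.0 under constant hazards: about 6–7% instead of 2.5% at a median of 6. That median is half as long again as planned.

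These sizes rest on the assumed medians and shapes and on reading 92% as the 10-minute proportion. The mismatch itself does not depend on the sizes. Section 11.1 also attaches the 1-minute label to another ratio ("The non-inferiority ratio is 0.75 (corresponding to margin of 1 minute"); which ratio is intended is a separate matter and does not decide this point. Severity: should-fix.

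**What to change.** 1. In section 11.2.5, write the hypotheses and the conclusion on the HR scale only, and remove the 1-minute median difference as an equivalent of the margin. Align section 4.1.2, which names the median as the primary outcome.
2. Pre-specify as supportive the Kaplan-Meier difference in medians with a 95% CI, and a check of proportional hazards.
3. Allow a statement that HemoStyp is within 1 minute of Surgicel in the median only if the upper 95% limit of the median difference itself is below 1 minute.
4. The difference in restricted mean time to 10 minutes may be reported descriptively, but must not carry that statement. With medians of 6 v 7 (exactly 1 minute worse), simulation at 118 per arm put its upper limit below 1 minute in about 23–25% of trials, against about 5–7% passing the current HR rule.

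**Cost.** Wording and standard outputs, with no extra subjects. The downside is that the 1-minute wording may not be supported. At the planned medians with constant hazards, the SE of a median is m/(ln 2 × √n). At 106 per arm this gives 0.42 and 0.56, so the SE of the difference is 0.70. The true difference is −1 minute, 2 minutes from the limit, so the probability of success is Φ(2/0.70 − 1.96), about 81% (85% at 118 per arm). Make the change before any outcome data are seen.
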